10.2 Notes

- a. "M protein" may also be known by the following synonyms: M-spike, monoclonal protein, myeloma protein, monoclonal paraprotein, M-component.
- b. Urine M protein measurement is estimated using 24-hour urine protein electrophoresis (UPEP) only. Random or 24 hour urine tests measuring kappa and lambda light chain levels are not reliable and are not recommended.

- c. Patients with 'measurable disease' in both the serum and urine (serum M protein $\geq 1\text{ g/dL}$ and urine M protein $\geq 200\text{ mg/24h}$) at baseline need to be followed by both SPEP and UPEP for response assessment.
- d. Both serum protein electrophoresis (SPEP) and urine protein electrophoresis (UPEP) must be conducted at timepoints indicated in [Section 9.0](#). Patients with serum M protein $\geq 1\text{ g/dL}$ and/or urine M protein $\geq 200\text{ mg/24h}$ at baseline will be assessed for response based on SPEP and/or UPEP results only. Except for assessment of Stringent Complete Response, serum free light chain (FLC) assay response requirements are only applicable to patients who had serum M protein $< 1\text{ g/dL}$, urine M protein $< 200\text{ mg/24 hrs}$, and an involved serum free light chain level $\geq 10\text{ mg/dL}$ at baseline. A normal serum free light chain ratio is required for all patients for a Stringent Complete Response.
- e. To qualify for a Complete Response, both serum and urine immunofixation must be carried out and must be negative, regardless of the size of the baseline M protein in the serum or urine.
- f. Skeletal survey is not required for assessment of response unless clinically indicated, but is recommended once a year in clinical practice. Stringent Complete Response, Complete Response, Very Good Partial Response, Partial Response, and Stable Disease all require no known evidence of progressive or new bone lesions if radiographic studies were performed, but radiographic studies are not required to satisfy these response requirements.
- g. The size of the soft tissue plasmacytomas is defined as the sum of the products of the cross-diameters of each plasmacytoma. The size of the bone lesions will be determined in a similar manner. A definite increase in the size is defined as a $\geq 50\%$ increase (and at least 1 cm^2) of this sum.

10.3 Best Response

This is calculated from a sequence of Objective Status (see [Section 10.1.b](#)) evaluations

Stringent Complete Response (sCR): An objective status of Stringent Complete Response on at least two sequential disease assessments. Only one bone marrow biopsy, done during one of these two disease assessments, is required to confirm the response.

Complete Response (CR): An objective status of Complete Response on at least two sequential disease assessments. Only one bone marrow biopsy, done during one of these two disease assessments, is required to confirm the response.

Very Good Partial Response (VGPR): An objective status of Very Good Partial Response on at least two sequential disease assessments.

Partial Response (PR): An objective status of Partial Response on at least two sequential disease assessments.

Unconfirmed SCR (UsCR): One objective status of Stringent Complete Response (based on evidence from serum and urine studies and, if drawn, bone marrow biopsy) but the confirmation studies are either not done, or when done, do not meet the requirements necessary to confirm response. This must be documented before progression and at least three weeks after registration.

Unconfirmed CR (UCR): One objective status of Complete Response (based on evidence from serum and urine studies and, if drawn, bone marrow biopsy) but the confirmation studies are either not done, or when done, do not meet the requirements necessary to confirm response. This must be documented before progression and at least three weeks after registration.

Unconfirmed VGPR (UVGPR): One objective status of Very Good Partial Response, but the confirmation studies are either not done, or when done, do not meet the requirements necessary to confirm response. This must be documented before progression and at least three weeks after registration.

Unconfirmed PR (UPR): One objective status of Partial Response, but the confirmation studies are either not done, or when done, do not meet the requirements necessary to confirm response. This must be documented before progression and at least three weeks after registration.

Stable / No Response (STA): At least one objective status of Stable at least three weeks after registration, but not qualifying as any of the above. If radiographic studies were performed there should be no known progressive or new bone lesions.

Increasing Disease (INC): First objective status recorded (other than Unknowns or those before three weeks) of Progression, provided this occurs within eight weeks of registration.

Inadequate Assessment. Response Unknown (NASS): Progression greater than eight weeks after registration and either all objective statuses prior to registration are unknown or the only known objective statuses occurred less than three weeks after registration.

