10.0 CRITERIA FOR EVALUATION AND ENDPOINT ANALYSIS

10.1 Response Criteria

Multiple Myeloma:

For the purpose of establishing one set of criteria for both Phase II and Phase III multiple myeloma studies, the following definitions will be used. These definitions are based on the International Uniform Response Criteria for Multiple Myeloma.

a. **Measurable Disease:** Measurable, quantifiable protein criteria must be present. Acceptable protein criteria are:

- Serum M protein ≥ 1 g/dL (≥ 10 g/L), quantified by using densitometry on serum protein electrophoresis (SPEP).

AND / OR

- Urine M protein [Bence-Jones Protein] ≥ 200 mg/24 hrs (≥ 0.2 g/24 hrs), quantified by 24-hour urine protein electrophoresis (UPEP, see Section [10.2.b](#)).

AND / OR

- Bone marrow plasma cells $\geq 30\%$

OR

- Patients who have both serum M protein levels < 1 g/dL AND urine M protein levels < 200 mg/24 hrs at baseline may be followed by serum free light chain (FLC) assay if involved free light chain level ≥ 10 mg/dL (≥ 100 mg/L).

Oligosecretory and Non-secretory Disease: Patients that do not meet the criteria for measurable disease above will be ineligible for this study.

b. **Objective Status:**

Stringent Complete Response (sCR):

- Meets all of the criteria for Complete Response (CR) and
- normal serum free light chain ratio and
- absence of clonal cells in bone marrow by immunohistochemistry or immunofluorescence

Complete Response (CR):

- Disappearance of all evidence of serum and urine M proteins on immunofixation electrophoresis studies **and**
- $< 5\%$ plasma cells in bone marrow **and**
- disappearance of any soft tissue plasmacytomas

Very Good Partial Response (VGPR):

- Meets all of the criteria for Partial Response (PR) **and**
- Serum and urine M proteins detectable by immunofixation but not on electrophoresis **or**
- $\geq 90\%$ reduction in serum M protein and urine M protein < 100 mg/24 hrs.

Partial Response (PR):

- If the patient had soft tissue plasmacytomas present at baseline and they were assessed at this disease assessment: $\geq 50\%$ reduction in size of soft tissue plasmacytomas (see Section [10.2.h](#)) **and**
- If the patient had $\geq 30\%$ plasma cells in bone marrow at baseline and a bone marrow biopsy was done: $\geq 50\%$ reduction in plasma cells **and**
- $\geq 50\%$ reduction in serum M protein and reduction in urine M protein $\geq 90\%$ or to $< 200 \text{ mg/24hr}$ **or**

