11.5 Analysis of Secondary Endpoints

Secondary efficacy endpoints include response rate (PR or better) and overall survival (OS). All efficacy analyses will be performed on intent to treat basis. The response rate (sCR, CR, VGPR, PR) for each arm will be determined by the number of patients achieving a response as defined in Section [10.3](#) divided by the number of patients assessed for response in each arm and compared between arms using Fisher's exact test.

The response rate for patients who relapse on Arm 1 and cross-over to Arm 3 will also be determined in order to determine whether response can be re-captured for those patients by increasing the carfilzomib dose.

Overall survival will be assessed in each arm using the method of Kaplan Meier and compared using the stratified log-rank test.

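### Section 10.3 confirms a response only by the same category twice in a row, so some patients at PR or better on consecutive assessments are counted as non-responders

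*Combined protocol and SAP*

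**What the plan says.** Section 10.3 derives best response from the series of assessments: "This is calculated from a sequence of Objective Status" evaluations. Each confirmed category then repeats one form:

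- PR: "An objective status of Partial Response on at least two sequential disease assessments".
- VGPR: "An objective status of Very Good Partial Response on at least two sequential disease assessments".
- CR: "An objective status of Complete Response on at least two sequential disease assessments". The sCR entry is parallel.

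Each level also has an unconfirmed category. For PR the entry opens: "One objective status of Partial Response, but the confirmation studies are either not done, or when done, do not meet the requirements necessary to confirm".

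Section 11.5 names the secondary endpoint as PR or better and defines it so: "The response rate (sCR, CR, VGPR, PR) for each arm will be determined by the number of patients achieving a response as defined in Section". The reference there is to Section 10.3, and the denominator is the patients assessed for response. The arms are compared by Fisher's exact test. The parenthetical list contains no unconfirmed category. Section 11.5 also asks for a response rate among patients who cross over to Arm 3.

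**The concern.** The label and the derivation disagree. A patient at PR on one assessment and VGPR on the next has been at PR or better twice running, and the deeper second result supports the first. Yet neither category has been recorded twice in a row. If progression or removal follows, the written rule leaves the patient unconfirmed. That patient stays in the denominator and is missing from the numerator. A patient with two flat PRs before progression counts as a responder.

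At stake is the between-arm comparison of a secondary efficacy endpoint. The Arm 3 rate, meant to show whether a higher dose recaptures response, is also at stake if it is derived in the same way.

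**Working it through.** The plan states no expected response rate or power for response, so there is no figure of its own to reproduce. The check has three steps.

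**1. Apply two rules to example sequences.** Rule A is Section 10.3 as written: the same status at two consecutive assessments. Rule B is 'or better': two consecutive statuses at or above the level.

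| Sequence | Rule A | Rule B |
|---|---|---|
| PR, PR, PROG | PR | PR |
| PR, VGPR, PROG | unconfirmed | PR |
| PR, VGPR, CR, PROG | unconfirmed | VGPR |
| CR, sCR, PROG | unconfirmed | CR |
| VGPR, PR, PROG | unconfirmed | PR |
| PR, PR, VGPR, PROG | PR | PR |
| PR, VGPR, VGPR, PROG | VGPR | VGPR |

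**2. Find how far the loss can reach.** Take a run of k response assessments that never worsens. Rule A misses it only if every step goes strictly upward. With four levels there are C(4,k) such runs, out of C(k+3,k) non-worsening runs:

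- k = 2: 6 of 10
- k = 3: 4 of 20
- k = 4: 1 of 35
- k = 5: 0 of 56

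These count patterns and are not probabilities. From the fifth non-worsening response assessment some level must repeat, so no such patient is lost. Rule B loses none at any k of 2 or more.

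**3. Illustrate the size.** Every rate in this step is an assumption. At each monthly visit a patient leaves with probability x. One who stays moves from stable to PR with probability e. One already at PR or VGPR moves up one level with probability d. CR is the top level.

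| e, d, x | Rule B, 12 visits | Rule A, 12 visits | Loss, 12 visits | Loss, 24 visits |
|---|---|---|---|---|
| 12%, 20%, 6% | 53.7% | 52.6% | 1.1 | 0.9 |
| 12%, 20%, 10% | 43.1% | 41.9% | 1.2 | 1.1 |
| 15%, 35%, 6% | 60.4% | 58.0% | 2.3 | 1.9 |
| 15%, 35%, 10% | 49.0% | 46.4% | 2.6 | 2.4 |
| 15%, 50%, 6% | 60.4% | 56.7% | 3.7 | 3.0 |
| 15%, 50%, 10% | 49.0% | 44.9% | 4.1 | 3.8 |

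Losses are in percentage points, from unrounded values. Of 63 patients per arm (Section 11.2), 1.1 points is 0.7 patient and 4.1 points is 2.6 patients.

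A hand check with unlimited visits: a patient reaching PR is lost with probability (1−x)·d·x·[1 + (1−x)·d]. The chance of ever reaching PR is (1−x)e / [1 − (1−x)(1−e)]. For the last row, 0.9 × 0.5 × 0.10 × 1.45 = 0.0653, and 0.135/0.235 = 0.574. The product is 3.7 points, close to the 3.8 at 24 visits.

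**Between arms.** That expression rises with both d and x over the ranges used here, so an arm that deepens faster but leaves more slowly may lose more or less. The design medians in Section 11.2, 9 and 15 months, give exit rates per 28-day cycle of 1 − 0.5^(28/(9 × 30.44)) = 6.8% and 1 − 0.5^(28/(15 × 30.44)) = 4.2%. Assume e = 12% in Arm 1 and 15% in Arm 2, with 24 visits:

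- Deepening 20% in both arms: loss 0.96 in Arm 1, 0.77 in Arm 2.
- Deepening 35% in both: 1.87 and 1.50.
- Deepening 20% and 35%: 0.96 and 1.50, about 0.5 point more in Arm 2.
- Deepening 20% and 50%: 0.96 and 2.38, or 1.42 points more in Arm 2. That is 1.42% × 63 = 0.9 patient.

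**The case against.** The best defence is that the criteria are nested. In Section 10.1b the VGPR entry begins "Meets all of the criteria for Partial Response (PR", and the sCR entry begins "Meets all of the criteria for Complete Response (CR) and". A VGPR at the second assessment therefore satisfies the PR criteria and could be said to confirm the PR. The PR-or-better label in Section 11.5 points the same way, and no sentence in Section 10.1b says that the statuses are exclusive. This has force: the defect may be in the wording and not in how the analysis is programmed. It does not settle the matter. Section 10.3 works from recorded statuses, keeps a separate unconfirmed category for each level, and never says that a deeper status confirms a shallower one. CR is not written as meeting the VGPR or PR criteria. Two programmers could derive different response rates from the same data.

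Two features of the plan reduce the loss. The note closing Section 10.1b lets the second assessment be done at any time, so a prompt repeat can confirm PR before it deepens. Footnote 11 of the study calendar continues assessments monthly after Cycle 12 until progression, so some late responders are confirmed after treatment ends. The 24-visit column reflects the second feature. The first is not modelled. In the other direction, footnote 13 no longer requires response assessments after removal for toxicity.

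A reader might infer that any patient whose response deepens is lost. The documents do not support that: PR-PR-VGPR and PR-VGPR-VGPR are both confirmed.

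**Conclusion.** The point stands as a gap in the written rule. On a literal reading, patients at PR or better on consecutive assessments are non-responders if no category repeats at consecutive assessments. This mainly concerns patients with few assessments between first response and progression or the end of assessment.

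The share lost cannot be derived from the documents. The 1 to 4 points rest on assumed entry, deepening and exit rates and 12 monthly visits, and shrink with longer follow-up.

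A reader might also infer a bias against Arm 2, on the view that the higher dose gives faster deepening. The documents give no deepening rates by arm, and slower exit, as the PFS design assumes for Arm 2, works the other way. With equal deepening the illustration shows a smaller loss in Arm 2. Its direction is not established.

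The effect is limited to the secondary response rate and, if the same definition is used, the Arm 3 rate. The primary PFS analysis does not use confirmed best response. The correction is worth making because the endpoint's label and derivation should agree, and it costs almost nothing.

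**What to change.** In Section 10.3:

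- Confirmed CR: CR or sCR at two or more consecutive assessments, without qualifying for confirmed sCR.
- Confirmed VGPR: VGPR or better at two or more consecutive assessments, without qualifying for a higher confirmed category.
- Confirmed PR: PR or better on the same terms.
- Unconfirmed categories: only for patients without two consecutive assessments at PR or better.

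In Section 11.5, state that unconfirmed categories are not counted as responses, and whether the Arm 3 rate follows the same rule.

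The cost is a few words in each section and a small change to the derivation program. No new data are needed, so it can be settled in the analysis specification although accrual is closed.

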10.4 Time to Death

From date of registration to date of death due to any cause. Patients last known to be alive are censored at date of last contact.

10.5 Progression-Free Survival

From date of registration to date of first documentation of progression or symptomatic deterioration (as defined below), after having received the full-assigned Arm-specific dose of carfilzomib (27 mg/m² or 56 mg/m²), or death due to any cause. Patients last known to be alive and progression-free are censored at date of last contact.

Symptomatic Deterioration: The global deterioration of health status requiring discontinuation of treatment without objective evidence of progression.

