CHAIR
[name]
[name]
[name]
[contact]
[contact] FAX

RE: **S1304**, "A Phase II Randomized Study Comparing Two Doses of Carfilzomib (NSC-756640) with Dexamethasone for Multiple Myeloma Patients with Relapsed or Refractory Disease". Study Chairs: Drs. [name], [name], [name], [name] and [name].

MEMORANDUM

Study Chair: [name]
[contact]
E-mail: [contact]

IRB Review Requirements

() Full board review required. Reason:
() Initial activation (should your institution choose to participate)
() Increased risk to patient
() Complete study redesign
() Addition of tissue banking requirements
() Study closure due to new risk information

() Expedited review allowed

(✓) No review required

MEMORANDUM

The purpose of this memorandum is to clarify the intent of the protocol as it pertains to interpretation of the patient having received the "full assigned dose" and the associated course of treatment in event of progression while still on Cycle 1 for both Arm 1 and Arm 2 of the protocol.

The intent of the protocol is that for both Arm 1 and Arm 2 the "full assigned dose" is achieved in Cycle 2, wherein, the "full assigned dose" for Arm 1 is 27 mg/m² and the "full assigned dose" for Arm 2 is 56 mg/m².

Herein, this memorandum provides the following additional clarifications to the protocol:

- If a patient progresses prior to completion of Cycle 1 on either Arm 1 or 2, the patient should continue on protocol therapy through Cycle 2.
- If a patient randomized to Arm 1 progresses on or after Cycle 2, then the patient will be eligible for crossover to Arm 3.
- If a patient randomized to Arm 2 progresses on or after Cycle 2, then the patient will be removed from the protocol.

These clarifications will be addressed in a forthcoming revision to Sections 5.2, 5.2d, 7.1d, 7.2, and 10.5 of the protocol.

This memorandum serves to notify the NCI, Alliance, ECOG-ACRIN, and the SWOG Statistical Center.

cc: [name].
[name], M.S.
[name]
[name], M.R.T.
[name] – Alliance
[name] – ECOG-ACRIN
[name] – ECOG-ACRIN
[name] – Biologics
[name] – Onyx

CLOSED/EFFECTIVE 05/15/2016

Distribution Date: April 1, 2015
 CTEP Submission Date: March 12, 2015

GROUP CHAIR'S OFFICE

[name]
CHAIR
 [name]
 [name]
 [name]
 [contact]
 [contact] FAX

TO: ALL NATIONAL CLINICAL TRIALS NETWORK MEMBERS; CTSU

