7.1 General Considerations

- a. Patients must have creatine kinase (CK), cardiac-specific troponin T (TnT) and/or troponin I (TnI) testing—both TnT and TnI preferred if available, creatine kinase-MB (CK-MB), brain natriuretic peptide (BNP) and/or proBNP performed on Cycle 1, Day 1. See [Section 9.0](#) for additional timepoints. In the event that Cycle 1, Day 1 laboratory tests are resulted and the patient no longer meets one or more of the eligibility criteria, treatment must be held. Laboratory tests and any associated supportive care must be repeated. If the repeat lab results fall within the eligibility criteria, treatment may be resumed. In the event that treatment must be held for \geq 28 days, the patient must be removed from the protocol.
- b. Patients on Arm 1 will receive dexamethasone/low-dose carfilzomib for up to 12 cycles or until progression that occurs after the start of Cycle 2, whichever comes first. If patient progresses after the start of Cycle 2 and prior to completion of 12 cycles, the patient will cross-over and be registered to Arm 3 where they may receive up to an additional 12 cycles of treatment.
- c. Results of Day 1 laboratory tests are not required prior to starting treatment for each cycle subsequent Cycle 1 (see Section 7.1a for instructions regarding D1, C1 results). If lab results are abnormal or indicative of adverse events, the treating physician should refer to Section 8.0 for dose modifications, and Response Assessments should be conducted at time of dose modification and as indicated in [Section 9.0](#). If dose modification is not indicated, the physician should otherwise continue treatment at physician discretion.
- d. Patients on Arm 2 will receive dexamethasone/high dose carfilzomib for up to 12 cycles, or until progression that occurs after the start of Cycle 2, whichever comes first. If a patient progresses after the start of Cycle 2, the patient will discontinue protocol treatment.

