7.3 Registration Step 1 – Initial Registration (Arms 1 and 2)

a. Carfilzomib Dosing

For both treatment arms of the initial registration (Arms 1 and 2), carfilzomib will be administered at a dose of 20 mg/m^2 for Cycle 1. If tolerated in Cycle 1, the dose will be escalated to 27 mg/m^2 (Arm 1) or 56 mg/m^2 (Arm 2) beginning in Cycle 2 and continued in subsequent cycles. Note: Dose rounding is acceptable at the discretion of the treating physician; this must be documented on the **S1304** Treatment Form.

The carfilzomib dose will be calculated using the patient's actual body surface area at baseline. Patients with a body surface area greater than 2.2 m^2 should receive a dose based upon a body surface area of 2.2 m^2 . Dose adjustments do not need to be made for weight changes of less than or equal to 20%.

If a patient experiences any Grade 3 or 4 non-hematologic toxicity or Grade 4 hematologic toxicity in Cycle 1 that is considered to be related to study treatment, the second cycle of treatment will be given with carfilzomib at 20 mg/m^2 prior to escalation to the respective treatment dose for subsequent cycles. If a patient cannot undergo the dose escalation to the treatment dose despite being at 20 mg/m^2 for 2 cycles, they will be removed from protocol therapy.

b. Arm 1 – Dexamethasone + Low Dose Carfilzomib

Agent	Dose	Route	Day	Schedule*
Dexamethasone ^b	20 mg	IV	1, 2, 8, 9, 15, 16	up to 12 cycles
Carfilzomib ^a	20 mg/m^2	IV over 2-10 mins	1, 2, 8, 9, 15, 16	Cycle 1
Carfilzomib	27 mg/m^2	IV over 2-10 mins	1, 2, 8, 9, 15, 16	Cycles 2-12

* Note: 1 cycle = 28 days

^a See Section [7.3a](#) for Cycle 1 carfilzomib dosing and for dose capping based on BSA.

^b On all treatment days, dexamethasone will be administered 30 minutes prior to the carfilzomib infusion.

c. Arm 2 – Dexamethasone + High Dose Carfilzomib

Agent	Dose	Route	Day	Schedule*
Dexamethasone ^b	20 mg	IV	1, 2, 8, 9, 15, 16	up to 12 cycles
Carfilzomib ^a	20 mg/m^2	IV over 2-10 mins	1, 2, 8, 9, 15, 16	Cycle 1
Carfilzomib	56 mg/m^2	IV over 30 mins	1, 2, 8, 9, 15, 16	Cycles 2-12

* Note: 1 cycle = 28 days

^a See Section [7.3a](#) for Cycle 1 carfilzomib dosing and for dose capping based on BSA.

^b On all treatment days, dexamethasone will be administered 30 minutes prior to the carfilzomib infusion.

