7.6 Criteria for Removal from Protocol Treatment

- a. Progression of disease or symptomatic deterioration (as defined in Section [10.5](#)) **for patients being treated with higher dose (56 mg/m²) carfilzomib.**
- b. Completion of 12 cycles of low dose carfilzomib on Arm 1 or 12 cycles of high dose carfilzomib.
- c. Unacceptable toxicity.
- d. Patient is unable to dose-escalate to assigned dose (27 mg/m² or 56 mg/m²) after 2 cycles of therapy.
- e. Permanent discontinuation of carfilzomib.
- f. Treatment delay for any reason > 4 weeks.
- g. The patient may withdraw from the study at any time for any reason.

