8.3 Dose Reductions for Toxicity

a. Carfilzomib

If a patient experiences any Grade 3 or 4 non-hematologic toxicity or Grade 4 hematologic toxicity in Cycle 1 that is considered to be related to study treatment, the second cycle of treatment will be given with carfilzomib at 20 mg/m^2 prior to escalation to the respective treatment dose for subsequent cycles. If a patient cannot undergo the dose escalation to the treatment dose despite being at 20 mg/m^2 for 2 cycles, they will be removed from protocol therapy.

Patients experiencing \geq Grade 3 non-hematologic or Grade 4 hematologic toxicity considered related to carfilzomib will have their treatment held until toxicity has resolved to Grade 2 or better. Supportive care should be administered per local institutional guidelines. When the toxicity has resolved, treatment will resume per the following guidelines:

- If the toxicity is resolved with supportive care prior to the next scheduled dose, carfilzomib treatment will be resumed at the same dose level.
- If the toxicity does not resolve until after the next scheduled dose, carfilzomib will be resumed at the next lower dose level as outlined in the dose reduction table below.

	Arm 1	Arms 2 and 3
Assigned Dose	27 mg/m^2	56 mg/m^2
Dose Level -1	20 mg/m^2	45 mg/m^2
Dose Level -2	15 mg/m^2	36 mg/m^2

- For patients whose drug toxicity does not resolve to Grade 1 or better (with the use of adequate supportive care) after 4 weeks of holding treatment, or who experience \geq Grade 3 non-hematologic or Grade 4 hematologic toxicity at Dose Level -2 will be removed from protocol treatment.

b. Dexamethasone

In general, dose reduction of dexamethasone is not allowed. However, in the case of Grade 3 or 4 gastrointestinal bleeding, dexamethasone may be discontinued, depending on clinical judgment of the treating physician. In case of dexamethasone discontinuation, premedication guidelines as mentioned below should be used and carfilzomib therapy will continue. For other Grade 3 or 4 toxicities with dexamethasone (including Grade 3 or 4 hyperglycemia despite adequate treatment with anti-hyperglycemic measures including insulin) rather than discontinuing the drug, dose may be reduced by up to 50% if side effects persist despite administration of supportive care per local institutional standards.

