11.3 Analysis of Primary Endpoint

Efficacy analysis will be performed on intent to treat basis. Progression-free survival will be assessed in each arm using the method of Kaplan Meier and compared between arms using the stratified long-rank test. Assuming exponential progression-free survival, uniform recruitment of 72 patients a year, an accrual period of 1.75 years and a follow-up period of 1.5 years, 100 progressions are expected to occur within 3.25 years. The analysis for the primary endpoint will be performed after 100 progressions have been observed, but no later than 2 years follow-up of the last patient.

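### Section 10.5 counts progression as a PFS event only after the full assigned dose, so observed progression in a living patient who never receives that dose drops out of the intent-to-treat primary analysis

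*Combined protocol and SAP*

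**What the plan says.** - **Event (Section 10.5).** PFS runs from registration to first documented progression or symptomatic deterioration "after having received the full-assigned Arm-specific dose of carfilzomib" (27 or 56 mg/m²), or to death from any cause. The dose condition does not apply to death.
- **Censoring (Section 10.5).** "Patients last known to be alive and progression-free are censored at date of last contact".
- **Analysis (Section 11.3).** "Efficacy analysis will be performed on intent to treat basis", by Kaplan-Meier and a stratified log-rank test, at 100 progressions or at most 2 years after the last patient.
- **Patients who may never receive the assigned dose.** Both arms start at 20 mg/m². After specified related toxicity in Cycle 1, "the second cycle of treatment will be given with carfilzomib at" 20 mg/m² (Section 8.3a; also 7.3a). "If a patient cannot undergo the dose escalation to the treatment dose despite being at" that level for two cycles, the patient is removed from protocol therapy (Section 7.3a). Section 7.6d lists the same reason for removal: "Patient is unable to dose-escalate to assigned dose".
- **Treatment trigger (Sections 7.1b and 7.1d).** Treatment continues up to 12 cycles or "until progression that occurs after the start of Cycle 2, whichever comes first". This is keyed to the cycle, not to the dose received. The memorandum of April 1, 2015 gives the link: the full dose "is achieved in Cycle 2".

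**The concern.** A patient who cannot escalate, progresses and is alive has no event under Section 10.5. Nor is the patient progression-free, so the censoring sentence fits only if that term is stretched to mean that no qualifying event has occurred. An observed progressor would then stay in the risk set. No other section supplies a rule.

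Whether a progression counts in the primary comparison thus turns on something that happens after randomisation. The analyst must either drop an observed progression or choose a rule once the data exist. The choice also affects when the 50-progression futility look (Section 11.4) and the 100-progression trigger (Section 11.3) are reached.

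Three limits apply:
- Death still counts for everyone.
- A Cycle 1 progressor who later receives the full dose has a delayed event, not a lost one.
- A patient with no documented progression is covered by the existing censoring rule.

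**Working it through.** **1. The texts side by side.** Section 10.5 requires receipt of the assigned dose; Sections 7.1b and 7.1d require only that Cycle 2 has started. The April 2015 memorandum shows these were meant to coincide. They separate for a patient held at 20 mg/m² in Cycle 2: progression then meets the 7.1 trigger but is not a PFS event. Section 10.3 records increasing disease for progression within eight weeks of registration with no dose condition, so one observation can be progression for response but not for PFS.

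**2. The plan's own figures (Sections 11.2 and 11.3).** Inputs: 63 per arm, medians 9 and 15 months, hazard ratio 1.67, one-sided alpha 0.1, 90% power, accrual 21 months, follow-up 18 months.
- Events needed (Schoenfeld): 4 × (1.2816 + 1.2816)² / (ln 1.67)² = 26.28 / 0.263 = 99.9, so 100.
- Probability of an event by month 39, with λ = ln 2 / median: 1 − [exp(−18λ) − exp(−39λ)] / (21λ) = 0.876 (Arm 1) and 0.721 (Arm 2).
- Expected events: 63 × 0.876 + 63 × 0.721 = 55.2 + 45.4 = 100.6.
- Power: Φ(√(100.6/4) × ln 1.67 − 1.2816) = 0.90.

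The stated 100 events and 90% power reproduce.

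**3. How many patients fall in the gap.** The documents do not give the share q who never receive the assigned dose. Assume 5, 10 or 15% per arm (about 3, 6 or 9 of 63), with the same progression hazard as other patients. Suppose median survival after progression is 12 months (assumed). Then 32.5% (Arm 1) and 29.4% (Arm 2) of affected patients have progressed and are alive at month 39; with 6 months it is 15.4% in both arms. Over both arms, 63q × (0.325 + 0.294) gives about 2, 4 and 6 patients, and 63q × (0.154 + 0.154) gives about 1, 2 and 3. For affected patients who have died, the event moves from progression to death.

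**4. Effect on the test.** Unstratified log-rank simulation, 12,000 trials per scenario, analysis at the 100th event or 24 months after last entry. With nothing lost, power is 0.893 (0.902 at a fixed 39 months) and the null rejection rate is 0.103. Monte Carlo standard error for power near 0.89 is √(0.89 × 0.11 / 12,000) ≈ 0.003.

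| Handling of affected patients | Power at q = 5 / 10 / 15% | Type I error |
|---|---|---|
| Later death counts, 12-month median | 0.877 / 0.866 / 0.846 | 0.105 / 0.095 / 0.104 |
| Later death counts, 6-month median | 0.888 / 0.882 / 0.872 | 0.099 / 0.100 / 0.100 |
| Censored at progression | 0.891 / 0.887 / 0.876 | 0.106 / 0.102 / 0.103 |
| Outer bound: no affected patient dies | 0.836 / 0.783 / 0.708 | 0.102 / 0.099 / 0.099 |

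In the first row the mean analysis time moves from month 38.3 to 39.6, 40.8 and 41.9.

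**5. Unequal shares.** With no true difference and shares of 2/63 (Arm 1) and 3/63 (Arm 2), the rejection rate is 0.122, 0.109 and 0.117 for the first three rows. Reversed, it is 0.084, 0.092 and 0.087.

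**The case against.** **The dose condition was deliberate.** Revision #4 added it so that Cycle 1 progressors continue through Cycle 2. Counting every progression would record a primary event while the plan keeps the patient on treatment and before the doses differ. A narrower repair would add a rule for never-escalated patients only. That would close the gap, but the Revision #4 rationale concerns Cycle 1 progression and does not address patients who never escalate. A narrow rule would also leave the date of the primary event dependent on dose received.

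**Dilution.** Under the plan's exponential assumption, 6.8% of Arm 1 and 4.2% of Arm 2 progress within 28 days, about 4.3 and 2.6 of 63. If the Cycle 1 hazard is the same in both arms, power with all progressions counted is about 0.84–0.85. It is also about 0.84–0.85 if only the never-escalated gap is closed, and 0.82–0.85 under the current rule. The broader fix therefore costs no measurable power.

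**Intent to treat may govern only who is analysed and in which arm.** Section 10.5 indeed removes no patient. The conflict lies in the event definition: an observed progression in a randomised patient is disregarded because of exposure.

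**Small and unsourced effect.** This stands. The shares are assumptions, the documents show no difference between arms, and Cycle 1 dosing is the same in both.

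**Some progressions will not be seen.** This stands in part. Calendar footnote 13 ends required response assessments after removal for toxicity, a main route into the gap, so 1 to 6 patients is probably on the high side. Footnote 13 can be read as an exception to footnote 11, but its effect on ascertaining PFS still needs stating. Section 7.8 follows all patients to death or 3 years, and Section 14.4e collects the date and method of off-treatment progression.

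**Conclusion.** The concern holds. For a group the protocol itself foresees, Section 10.5 gives no event for an observed progression in a living patient, and its censoring rule does not cover that patient. The reading of the text needs no assumption. The size does: with 5 to 15% affected per arm, about 1 to 6 of 126 patients are in the gap, and power is 0.85 to 0.89 under the three realistic handlings, against about 0.89 with nothing lost. Values down to 0.71 arise only if no affected patient dies. Type I error is 0.095–0.106 with equal shares; it moves to about 0.11–0.12 or 0.08–0.09 only if the shares differ between arms, which the documents do not show. The reason to change is less the power loss than that an intent-to-treat primary event should not depend on dose received, and that correcting it is cheap.

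**What to change.** - In Section 10.5, define the primary intent-to-treat event as the first documented progression (Section 10.1b), symptomatic deterioration or death in every randomised patient, regardless of dose received. Settle this before the primary comparison is run.
- Report the present dose-conditional definition as a sensitivity analysis, with an explicit rule for patients who progress without having received the assigned dose.
- Reconcile Section 10.5 with the Cycle 2 trigger in Sections 7.1b and 7.1d, and calendar footnotes 11 and 13 with the PFS definition. No treatment rule is proposed.

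**Cost.** New wording and one sensitivity analysis; no new form or visit, given Sections 7.8 and 14.4e. There are two downsides. Events at the common 20 mg/m² starting dose, including those of Cycle 1 progressors, slightly dilute the dose contrast. Unless footnote 13 is reconciled, progression after removal for toxicity will be assessed less regularly than in other patients.
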